**Objective III-B. Effects of energy deficit and exogenous testosterone on the gut microbiome and intestinal permeability.**

[figure not shown]
The lining of the gastrointestinal tract is both a physical and immunological barrier, acting to protect the host by deterring translocation of potentially harmful bacteria,

toxins, and antigens into systemic circulation. The immunological barrier consists of several specialized cell types that secrete antimicrobial compounds and participate in antigen-sensing and immune response activation. The physical barrier includes both a mucus layer and a layer of epithelial cells connected by protein complexes known as tight junctions. Tight junctions are particularly important to the integrity of the physical barrier, acting to regulate permeability through the opening and closing of paracellular channels through which contents of the intestinal lumen can pass. Disruption or dysfunction of the gastrointestinal barrier can increase intestinal permeability, causing translocation of bacteria and their pro-inflammatory components (e.g., lipopolysaccharide [LPS], also known as endotoxin) into systemic circulation. The resulting low-grade systemic inflammation increases susceptibility to acute and chronic disease, and may compromise nutrient status (e.g., iron status), adversely impact cognitive and physical performance, and exacerbate gastrointestinal barrier dysfunction.

Evidence suggests that changes in gut microbiota due to energy deficit may alter intestinal permeability (Figure 1). Specifically, gut bacteria capable of degrading host-derived glycans within the mucus layer outcompete other bacteria populations as energy restriction decreases the availability of undigested dietary substrates. Sulfates released during degradation of mucins within the mucus layer facilitate the growth of pro-inflammatory, sulfate-reducing bacteria, which can lead to decreased bacterial fermentation and short-chain fatty acid (SCFA) production. The resulting increase in colonic pH is conducive to the growth of pathogenic bacteria that suppress antimicrobial protein secretion and immune function. This combination of factors can degrade the mucus barrier, increase intestinal permeability, and subsequently affect inflammation and metabolic dysfunction. Additionally, reduced leptin secretion may alter intestinal permeability and gut microbiota composition during energy deficit as leptin stimulates gut mucin production, and reduced leptin concentrations during energy deficit have been associated with changes in gut microbiota composition in mice.

Emerging evidence suggests testosterone may mediate intestinal permeability. Specifically, sex hormones, including testosterone, increase expression of tight junction proteins in multiple tissues. Testosterone is also thought to regulate immunity, with recent evidence indicating that testosterone may have a bi-directional relationship with the gut microbiome. These findings suggest that testosterone maintenance could attenuate energy deficit-mediated decrements in gut microbiota composition and intestinal permeability. To our knowledge, this hypothesis has not been empirically examined. This study will address this knowledge gap by determining the effects of energy deficit and testosterone maintenance during energy deficit on the gut microbiome, intestinal permeability, and inflammation.

**Figure 1. Proposed mechanisms of energy deficit-mediated effects on the gut microbiome and intestinal permeability.**

### Experimental Design and Overview

[figure not shown]
Physically active men (n=60) will be recruited for a 3-phase, randomized, placebo-controlled study to assess physiological and psychological responses to testosterone administration, at a dosage designed to maintain eugonadal status, during severe and sustained energy restriction. **Free-living, phase 1** will begin immediately after baseline measures are complete. Participants will be prescribed and provided individualized, 14-day eucaloric lead-in diets with  $1.6 \text{ g protein} \cdot \text{kg}^{-1} \cdot \text{d}^{-1}$ , 30% of total daily energy requirements from fat, and the remaining energy from carbohydrate. The 14-day lead-in diet will ensure sufficient time to acclimate to the prescribed study diet. After completing phase 1, participants will be randomly assigned to one of two, highly controlled (**live-in, phase 2**), 28-day treatment groups: energy deficit (DEF, 55% of total daily energy expenditure, TDEE) or energy deficit + testosterone maintenance (DEF+TEST). Protein intake ( $1.6 \text{ g protein} \cdot \text{kg}^{-1} \cdot \text{d}^{-1}$ , based on day 14 total body mass) will remain constant throughout the 28-day intervention, fat will contribute 30% of total energy, and the remaining energy will be derived from carbohydrate. Exercise-induced energy expenditure (EIEE) will be increased 50% above TDEE for all participants. Energy intake will be 45% of the elevated TDEE, resulting in a 55% energy deficit (see Table 1 for an example).

**Table 1.** Example total daily energy expenditure and dietary energy and macronutrient content of the 28-d experimental diets.

Days 0-14		Days 15-42	
BMR+TEF	2250	TDEE days 0-14	2500
EIEE	250	50% ↑ EIEE	1250
TDEE	2500	TDEE for all groups	3750
Energy intake, deficit, diet composition, and estimated loss of body mass during days 15-42			
TDEE		DEF, DEF+TEST	
Energy intake, kcal (% of TDEE)		3750	
Energy deficit, kcal (% of TDEE)		1687 (45)	
Protein, g (g/kg, kcal)		2063 (55)	
Fat, g (% total energy, kcal)		128 (1.6, 512)	
Carbohydrate, g (g/kg, kcal)		56 (30, 506)	
Body mass loss, kg (% of initial body mass)		168 (2.1, 670)	
		7.5 (9.4)	

Representative data based on a 2500 kcal TDEE for an 80 kg male for days 0-14.

Participants will be released from the metabolic center the day after completing phase 2. Participants will be allowed to return to their habitual diet and physical activity patterns to assess total body mass and, more importantly, skeletal muscle mass recovery from the intervention (**free-living, phase 3**). Recovery will be assessed after completing phase 2 to determine when body mass has been recovered within  $\pm$  2.5% of initial body mass (end of study, EOS). The duration of phase 3 will vary by participant, depending on each individual's rate of body mass regain (42-day maximum for phase 3). The experimental design is presented in **Figure 2**.

Details regarding study procedures can be found in the *Study Parameters & Procedure Descriptions* section below. See **Appendix A** Train Schedule for timing of study-specific measures.

Enrollment will begin during the spring of 2016 and we anticipate enrollment to continue for at least one year (summer 2017).

We expect that all data will be collected by September 2017. Complete data analysis, including the preparation of the final report and peer-reviewed manuscripts, will be completed in the winter of 2018.

### Rationale for Duration and Severity of Energy Deficit

The duration and severity of energy deficit proposed in the current study was based on prior studies showing decrements in testosterone concentrations during energy deficit (unpublished data, [name] 2015). Special operations field training has been shown to decrease testosterone levels by 50-85% and total body mass by 6-16% in response to short (7 days) and longer-term (56 days) energy deficits of  $\geq 1,000$  kcal/d (unpublished, [name] 2015). A tightly controlled clinical trial that reduced energy intake by ~750 kcal/d (40%) for 21 days produced smaller reductions in testosterone (16%) and total body mass (4%). Study duration, physical activity quantity and intensity, energy deficit, and dietary composition are critical factors to consider when comparing results from field and clinical studies. Therefore, in the current study, we have proposed a 28-day energy deficit that increases energy expenditure (+50%) and decreases energy intake (-55%) to levels comparable to the extreme energy deficits observed in military field studies. An energy deficit of this magnitude should produce

reductions in total body mass, lean body mass, and testosterone large enough for the intervention to be effective and create a biologically relevant and statistically significant difference between treatment groups.

### **Primary Study Endpoint**

Total body mass will serve as the primary study endpoint and be used as a daily measure of accuracy and compliance with the diet and exercise intervention. Recovery of total body mass to pre-deficit levels ( $\pm 2.5\%$ ) or 42 days in phase 3 without recovery of body mass to pre-deficit levels will signal EOS. No other endpoint will signal EOS for any particular participant.

However, the study may be terminated if a participant withdraws, is unable to complete the prescribed exercise, has complications after undergoing the biopsy procedure, or if there is proof of noncompliance. Participants are required to complete all study measures at the given time points. In the event a procedure cannot be completed or is refused, participant continuation in the trial will be determined by the PI and MI. Noncompliance to the intervention will be addressed on a case by case basis.

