### Power analysis

Relevant data (means  $\pm$  standard deviations) demonstrating the effects of moderate-to-severe energy deficit on lean body mass were used to determine statistical power and sample size. The percentage total body mass loss (2.7 kg) attributed to lean body mass during a 21-d, higher-protein (1.6 g·kg $^{-1}$ ·d $^{-1}$ ), moderate energy deficit was approximately 30% (0.8 kg). However, the proportion of total body mass loss (5.8 kg) attributed to lean body mass in response to a short-term (~7-d), military training-induced, severe energy deficit was approximately 55% (3.1 kg) (unpublished data). Based on these results, and given the proposed study will induce a 55% energy deficit for 28 days in men consuming a higher-protein diet (1.6 g·kg $^{-1}$ ·d $^{-1}$ ), lean body mass will likely account for 40% of the total body mass loss. Maintaining testosterone within normal physiological ranges is expected to attenuate the loss of lean body mass by 25%, such that those assigned to the testosterone group will lose proportionally 30%, the same percentage of lean body mass as demonstrated in our previous study. Based on these estimates, the sample size necessary to determine the estimated differences between treatments is 22 per group. However, based on previous variability in lean body mass loss in response to moderate-to-severe energy deficit, 25 participants per group is a more conservative estimate to allow for detection of treatment effects in the current study. To account for possible attrition (20%), 30 participants will be assigned to each group (60 total participants). To successfully enroll 60 participants, we request the ability to consent up to 240 participants, given only a third of those briefed and consented in past projects, with more lenient study-specific eligibility criteria, were enrolled. **At least 50 participants will complete the intervention and enrollment will stop once 50 participants have completed the study.**

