**Table 2. Power Analysis and Sample Size Justification**

**Hypothesized Effect (mean  $\pm$  SD)**

$\Delta$ Lean body mass following the 28-d intervention, kg	
DEF	$3.0 \pm 0.75$
DEF+TEST	$2.25 \pm 0.75$
Effect Size	1.0
Alpha	0.05
Power	0.90
Sample Size	22 per group
Expected variability	25 per group
20% study attrition	60 participants total
75% eligibility screen failure	240 total consented individuals

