### **Objective I: Statistics**

All data analyses will be based on the intention-to-treat principle using SPSS statistical software, unless otherwise noted. Data will be examined quantitatively and graphically for outliers and other artifacts that might have an undue impact on the analyses. Logarithmic or similar transformations will be applied when necessary to insure the validity of statistical procedures. All tests will be two-sided and considered statistically significant at  $p < 0.05$ .

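### Total body mass is labelled the primary endpoint, but the trial is sized on lean body mass, and the planning figures imply no group difference in total body mass

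*Combined protocol and SAP*

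**What the plan says.** The label is in the section Primary Study Endpoint: "Total body mass will serve as the primary study endpoint and be used as a daily measure of accuracy and compliance". The same section makes recovery of total body mass to within 2.5% of its pre-deficit level, or 42 days without recovery, the trigger for end of study (EOS). Nothing else in the protocol is called a primary endpoint. Objective II: Statistics uses the word primary only for certain ANOVAs. Objective I: Statistics applies one mixed model to body composition and all the other physiological outcomes, and singles out no variable, contrast or time point.

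The sample size rests on something else. The Power analysis says that data "demonstrating the effects of moderate-to-severe energy deficit on lean body mass were used to determine statistical power and sample size", and the variable in Table 2 is the change in "Lean body mass following the 28-d intervention, kg".

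The planning figures also describe total mass. Without testosterone, "lean body mass will likely account for 40% of the total body mass loss"; with it, "those assigned to the testosterone group will lose proportionally 30" per cent. Table 1 (Experimental Design and Overview) has one column for DEF and DEF+TEST together, with one deficit and one body mass loss, 7.5 kg (9.4%).

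**The concern.** A trial is judged on its primary endpoint, and the stated power should refer to that endpoint. Here the two have come apart.

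Total body mass is also a poor candidate for detecting a treatment effect in this design. Both arms are prescribed the same 55% deficit, and total mass is the daily check that the deficit was delivered, so the design works to make it equal between arms. At EOS it is held by rule to within 2.5% of its starting value unless 42 days pass first. Hypothesis I-A expects testosterone to reduce lean loss and to increase fat loss, which push total mass in opposite directions.

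If the label is taken at its word, a treatment that does exactly what is hoped would be expected to give a null primary result. A positive lean-mass result would then be one of many outcomes with no prespecified standing, and readers could fairly ask whether it was picked afterwards.

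**Working it through.** **Inputs.** From Table 2: lean-mass loss 3.0 kg (DEF) and 2.25 kg (DEF+TEST), SD 0.75 in each arm, alpha 0.05, power 0.90, 22 per group, raised to 25. From Objective I: Statistics: "All tests will be two-sided and considered statistically significant at" 0.05. From the Power analysis: lean share of total loss 40% (DEF) and 30% (DEF+TEST). From Table 1: deficit 2063 kcal/day, loss 7.5 kg, 80 kg man. The documents give no SD for change in total body mass.

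**Step 1. Reproduce the stated sample size.** Difference = 3.0 − 2.25 = 0.75 kg; standardised effect = 0.75/0.75 = 1.0.

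n per group = 2 (z₀.₉₇₅ + z₀.₉₀)² (SD/difference)² = 2 × (1.960 + 1.282)² × 1 ≈ 21.0, rounded up to 22.

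The two-sample t-test gives 22.02, with power 0.8997 at 22 per group and 0.934 at 25. A one-sided test would need 18, so the stated figure is two-sided. The 22 per group is correct, and it applies to lean body mass.

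**Step 2. Derive the planned loss of total mass.** Total loss = lean loss / lean share.

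- DEF: 3.0/0.40 = 7.5 kg
- DEF+TEST: 2.25/0.30 = 7.5 kg
- Planned difference: 7.5 − 7.5 = 0 kg

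**Step 3. Compare with Table 1.** 2063 × 28 = 57,764 kcal, and 57,764/7.5 ≈ 7,702 kcal per kg. Also 7.5/80 = 9.4%. So 7.5 kg is the body mass loss following from one deficit shared by both arms. Multiplying back, 40% × 7.5 = 3.0 and 30% × 7.5 = 2.25, which are the Table 2 means.

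**Step 4. Power for total body mass.** At a true difference of zero the chance of a significant two-sided result equals alpha, 5%, whatever the SD or sample size. No finite sample gives 90%.

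**Step 5. Sensitivity if the true difference is not zero.** The SD has to be assumed. With 25 per group and 90% power, the detectable difference in total mass is:

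| Assumed SD (kg) | Detectable difference (kg) |
|---|---|
| 0.75 | 0.70 |
| 1.0 | 0.94 |
| 1.5 | 1.40 |
| 2.0 | 1.87 |
| 2.5 | 2.34 |

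The plan gives no total-mass difference to set against this range.

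**The case against.** The strongest reply is that the section uses endpoint in an operational sense. Most of it concerns when a participant finishes, withdrawal and noncompliance, and it names no treatment comparison, time point or test. On that reading no primary test of total mass exists, the 5% describes an analysis the plan never defines, and lean mass would go through the same mixed model whatever the label. The Executive Summary and the sizing also make it plain which outcome the trial was built for.

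Secondly, the zero is inferred. Table 1 is an example for one 80 kg man, the 40% and 30% shares are a sizing simplification, and Hypothesis I-A gives no magnitudes. It also expects testosterone to maintain energy expenditure that restriction would otherwise lower, which under a fixed intake could make total losses differ. The Rationale for Duration and Severity of Energy Deficit lists total mass among the reductions expected to allow a significant group difference.

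Part of this stands. The operational reading may be what was meant; the zero and the 5% hold only under the planning figures; and offsetting lean and fat effects are an inference from those figures. But the sentence gives total mass two roles, primary endpoint and compliance measure. If only the second was intended, the protocol has no primary efficacy endpoint, and the same correction is needed. The Rationale section offers no total-mass difference. A non-zero difference would not rescue the label either, because total mass cannot tell spared lean tissue from lost fat.

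**Conclusion.** The concern holds. The only endpoint labelled primary is not the one the trial is powered for. The stated 0.90 power, correctly computed, belongs to lean body mass. Under the plan's own shares and Table 1, the expected group difference in total body mass is 0 kg, and the chance of a significant result on it is 5%, against 93% for lean mass at 25 per group (90% at 22). The 5% is conditional on those planning figures; the mismatch between the labelled and the powered endpoint is not. It should be corrected before unblinding because it decides what the trial formally tests.

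**What to change.** In the section Primary Study Endpoint, name change in DXA lean body mass from day 11 to day 39, DEF+TEST against DEF, as the single primary efficacy endpoint, tested at two-sided 0.05. In Objective I: Statistics, identify that contrast within the mixed model. Days 11 and 39 are the last scheduled scans before and during the deficit. Table 2 refers to the full 28 days and day 39 is the 25th of them (39 − 15 + 1), so the text should say that this scan stands for the end of the deficit. Keep total body mass as the daily compliance measure and EOS trigger, and report it as a secondary outcome. State that the power in Table 2 refers to the lean-mass endpoint.

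The cost is a documented amendment. The pages carry a December 2016 IRB approval and enrollment was planned from spring 2016, so the change may fall mid-trial. It would then need IRB approval, DSMB review as a major modification, and a date that precedes unblinding. Sample size, scans and procedures do not change.

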### **Recruitment Methods**

The PBRC staff has an extensive history of successfully recruiting and conducting large funded trials on exercise and dietary restriction interventions. Study recruitment will rely on previous methods, which have proven successful at enrolling volunteers who are consistent with the demographics of the region. PBRC also has a Clinical Trials Recruitment Core with 6 full-time staff dedicated solely to recruiting for clinical trials. In addition to phone calls, participants can screen via the PBRC website (<https://www.pbrc.edu/clinical-trials/>) and study-specific web pages are designed by the Recruiting Core. Both methods, phone and web, are funneled into a computerized participant-tracking system that allows for eligibility checks and real-time reporting. Investigators are able to track the recruitment status of their studies in real time using the PBRC intranet.

The metro Baton Rouge, LA, area has a population of 411,000. The Clinical Trials Recruitment Core receives 3,200 calls per month from potential volunteers. Study recruitment will rely on the existing methods of the Clinical Trials Recruitment Core to advertise via local media (print, radio, TV), paid targeted digital campaigns, earned media, social media (Facebook, Twitter, etc.), and collaborative relationships with local universities, sport vendors, health food vendors, etc. Targeted populations for recruitment will include PBRC employees, healthy adults (ages 18 and older), and non-military personnel.

### **Inclusion and Exclusion Criteria**

#### **Inclusion Criteria**

- Men aged 18-39 years
- Physically active (at least 2 days per week aerobic and/or resistance exercise)

- Not taking any prescription medications and/or willing to refrain from all medication use prior to and throughout the entire study period, unless provided/approved by the study physician
- Willing to refrain from alcohol, smoking, e-cigarettes or use of any nicotine product, caffeine, and dietary supplement use throughout the entire study period.
  - At the discretion of the study physician, wash-out period for medications, supplements, and over the counter medications (OTCs) is  $\geq$  1-4 weeks
  - Wash-out period for caffeine and alcohol is  $\geq$  7 days
- Willing to live on the PBRC inpatient unit for 28 consecutive days
- Willing to have a urine drug screening
- Meets age-specific US Army body composition standards according to Army Regulation 600-9, which includes estimates of percent body fat based on height, weight, and circumference measures (neck and waist)
- Total testosterone concentration is within the normal physiological range (300-1,000 ng/dL).

#### **Exclusion Criteria**

- Musculoskeletal injuries that compromise exercise capability
- Diagnosed cardiometabolic disorders (i.e., hypertension, hyperlipidemia, kidney disease, diabetes, etc.)
- Allergies or intolerance to foods, vegetarian practices, or history of complications with lidocaine
- Anabolic steroid, human growth hormone, or nutritional testosterone precursor-like supplement use within the past 6 months
- Will not refrain from smoking (any nicotine product), alcohol, caffeine, or any other dietary supplement during the study
- Any use of antibiotics, except topical antibiotics, within 3 months of study participation
- Colonoscopy within 3 months of study participation
- Chronic use of laxatives, stool softeners, antacids, or anti-diarrheal medications ( $\geq$  once a week)
- History of gastrointestinal disease (e.g., celiac, irritable bowel syndrome, colitis, Crohn's disease)
- Restrained eater (the Three-Factor Eating Questionnaire) as assessed by the study's psychological and behavioral assessment staff
- Adults unable to consent
- Women
- Prisoners
- Metal implants, claustrophobia, head size incompatible with MRI equipment, etc.
- Sedentary or engages in  $<2$  days of physical activity per week (aerobic and/or resistance training)
- Exceeds age-specific US Army body composition standards according to Army Regulation 600-9
- Previous history of kidney stones unless otherwise approved by the medical investigator
- Systolic blood pressure  $> 150$  or diastolic blood pressure  $> 95$  mmHg
- Previous history of breast or prostate cancer

- Previous history of COPD or Obstructive Sleep Apnea (OSA)
- Findings of lab results of PSA > 3ng/ml, Hematocrit > 50%, or positive urine drug screening
- Based on the investigative team's clinical judgment, a subject may not be appropriate for participation in the study.

Enrolling individuals based on US Army body composition standards (**Appendix B**) will ensure a population representative of the US military is studied.

